6.3 Sample Size

102 eligible subjects will be enrolled in this study across approximately 13 centers, with 51 subjects being enrolled in each product group. it is expected that each center will enroll between 8 and 15 subjects. If it is determined that ineligible subjects were enrolled (e.g. without denudement at baseline or leaving the study prior to the first assessment day), additional subjects will be enrolled so that a total of 102 eligible subjects will be enrolled in the study.

Page 16 of 54 Status: Release Version: 7 Issue Date: 8/31/2016 12:19:02 PM

6.4 Study Duration

In order to screen, enroll, and complete 102 evaluable subjects, an enrollment period of approximately 18-24 months is anticipated. Each adult subject may be followed for up to a maximum of 42 days or until the subject is discharged. Each pediatric subject may be followed for up to a maximum of 21 days or until the subject is discharged.

- 1. If the subject is discharged prior to 21 days, the subject will still have met the requirements for study completion.
- 2. Adult Subjects (>18years) can remain in the study for up to 21 days following enrollment receiving the Cavilon Advanced Skin Protectant or comparative product. All subjects will be discontinued at this point with the exception of the following 2 scenarios:
 - Subjects randomized to the comparative group, who fail to reach healing at the end of 21-day period with ongoing incontinence may be crossed over to the Cavilon Advanced Skin Protectant group and allowed to continue for up to an additional 21 days.
 - Subjects randomized to the Cavilon Advanced Skin Protectant group, who either re-epithelized or have a positive reduction in their IAD during the 21-day period, but remain hospitalized and continue to have incontinence, may continue to receive the Cavilon Advanced Skin Protectant product for up to an additional 21 days to evaluate prevention of IAD reoccurrence.
 - If a subject completely heals during the study, they may be discontinued at that time.
- 3. Pediatric Subjects Full term (37 weeks) to 18 years) can remain in the study for up to 21 days following enrollment receiving the Cavilon Advanced Skin Protectant product or comparative product. If the subject is discharged prior to 21 days, the subject will still have met the requirements for study completion.
 - Subjects randomized to the comparative group, who fail to improve (IAD) within 3 days of first application in the study may be crossed over to Cavilon Advanced Skin Protectant group and allowed to continue for up to an additional 21 days. The staff should cleanse the skin, complete skin assessments, and photographs prior to application of Cavilon Advanced Skin Protectant.
 - Subjects randomized to Cavilon Advanced Skin Protectant group, who fail to improve (IAD) within 3 days of first application in the study may be discontinued.
 - Subjects randomized to the product group, who either re-epithelized or have a positive reduction in their IAD during the 21-day period, but remain hospitalized and continue to have incontinence, may continue to receive the Cavilon Advanced Skin Protectant product for up to 21 days to evaluate prevention of IAD reoccurrence.
 - If a subject completely heals during the study, they may be discontinued at that time.

7. Study Endpoints

7.1 Primary Efficacy Endpoint

The primary efficacy endpoint will be percent change in IAD score from baseline to end of subject participation. The effect of skin protectants on clinical re-epithelialization of denuded skin in subjects with containment or resolution of urinary and/or fecal incontinence, as well as in subjects with ongoing urinary and/or fecal incontinence, will be observed. Skin condition will be determined using

clinical assessment data collected by means of a validated IAD skin assessment tool, and photographs.

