Outcome Measures:	Primary Efficacy Endpoint:
	The primary endpoint is percent change in IAD scores from baseline to end of study. Secondary Endpoint(s): Secondary end points will include: Time to re-epithelialization of denuded skin (defined as healing), time to progress from a severe Category 2 IAD to a Category 1 IAD or lower, avoidance of complications such as secondary infections and pressure ulcers efficacy in subjects who switch from the comparative group to the Cavilon Advanced Skin Protectant group after failure on the comparative group; Pain score comparison between the two products; Patient Quality of Life change from baseline; Nursing time; and Incontinence product use and associated cost.

Study Population:	Inclusion/Exclusion Criteria:								
	Subjects may be enrolled into this study if the answers to all these questions are yes .								
	 Is the subject a full term newborn (37 weeks or greater gestational age) or older? Is the subject in a facility providing nursing care 24 hours per day? Does the subject have severe Category 2 Incontinence-Associated Dermatitis-red with skin breakdown (i.e. skin erosion and denudation or denudation of skin alone) Is the subject willing to have photographs taken of their skin exposed to incontinence and permit use of photographs in potential publication? Is the subject willing to release rights to 3M for the use of the photos? Is there a reasonable expectation that the subject will remain in a facility for at least 7 days following enrollment in the study? Has the subject, or their legally authorized representative, signed an Institutional Review Board-approved informed consent/assent document and authorized the use and disclosure of protected health information? 								
	Subjects are excluded from participation in this study if any of the answers to these following questions is yes.								
	1. If female, is the subject pregnant or breast feeding or has she given birth within the 3 weeks preceding the screening visit?								
	2. Does the subject have a known allergy to acrylates or cyanoacrylates?								
	3. Does the subject have a Stage III, IV, unstageable, suspected deep tissue injury pressure ulcer in the area where the skin is affected by incontinence?								
	4. Does the subject have a preexisting skin disease on the areas affected by incontinence that may make skin assessments for this study difficult?								

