5.1 Primary Objective

The primary objective of this study is to compare the safety and efficacy of the recently 510(k) cleared product (3M[™] Cavilon[™] Advanced Skin Protectant), and to determine superiority compared to a commercially available moisture barrier paste with 15% zinc oxide (ConvaTec Sensi-Care[®] Protective Barrier), in the management of severe Category 2 Incontinence-Associated Dermatitis (red skin with denudement present) from urinary and/or fecal incontinence. The primary endpoint is percent change from baseline to end of study in IAD scores. Healing in this study is defined as reepithelialization of denuded skin.

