11.2 Final Study Visit

The subject's participation in this study is completed after 21-42 -days of follow-up or when the subject is discharged from the facility. At the final visit the following assessments will be completed:

- Medications
 - Review and record changes to current medications.
- Adverse Events
 - Assess and record adverse events. Immediately report any Serious Adverse Event. (Refer to Adverse Event CRF instructions).
- Perform Skin Cleansing and record pain score before and after cleansing
- Conduct Skin Assessment
- Take Photographs
- Administer Quality of Life questionnaire
- Healthcare Worker Ease of Use Survey
 - Complete end of study product Ease of Use survey
- Documentation
 - Complete and check all documentation.

Page 27 of 54 Status: Release Version: 7 Issue Date: 8/31/2016 12:19:02 PM

Page 28 of 54 Status: Release Version: 7 Issue Date: 8/31/2016 12:19:02 PM

Schedule of Events

Assessment	Screening/ Enrollment	D1 /23	D2 /24	D3 /25	D4 /26	D5 /27	D6 /28	D7 /29	D8 /30	D9 /31	D10 /32	D11 /33	D12 /34	D13 /35	D14 /36	D15 /37	D18 /38	D17 /39	D18 /40	D19 /41	D20 /42	D21 /43	End of Study/ D22/D44
Informed Consent	Х																						
Inclusion/Exclusion	Х																						
Urine Pregnancy Test	X																						
Demographics	X																						
IAD History & Current Product Use	х																						
Medications	Х	Х																					Х
Pressure Sore Risk Assessment	Х																						
Quality of Life questionnaire	x																						X
Skin Cleansing	X	Х	Х	Х	Х	Х	Х	Х	Х	Х	X	Х	Х	Х	Х	Х	Х	Х	Х	Х	Х	Х	Х
*Skin Cleansing – Timing & Product Use	х			X																			
Skin Assessment / IAD scoring	X	X		X		X			X		X		Х			X		X		X			X
Photographs	Х	Х		Х		Х			Х		X		Х			Х		Х		Х			Х
Sensi-Care Product Application Arm		х	X	X	Х	Х	X	X	X	Х	Х	Х	Х	Х	Х	Х	X	X	X	X	X		x
Cavilon Application		Х		Х		Х			Х		Х		Х			Х		Х		Х			
Clean Trace Assessment				X		Х			X		X		Х			Х		X		X			
*Product Application – Timing & Product Use				X																			
Healthcare Worker Ease of Use Survey		Х																					X
Incontinence Episode Care/Tracking		Х	X	X	Х	X	Х	Х	X	X	X	X	Х	Х	Х	X	X	X	X	X	Х	Х	X
Adverse Events		Х	Х	Х	Х	Х	Х	Х	Х	Х	Х	Х	Х	Х	Х	Х	Х	X	Х	Х	Х	Х	Х

* Only required for first Subjects in each product group

12. Subject Discontinuation

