19.1 Statistical Methods

19.1.1 Efficacy Analyses

The primary analysis will be the percent change from baseline to last visit in IAD scores. The IAD score at each time point will be estimated using the assessments at each time point. The percent change from baseline will be calculated at the last visit and compared between treatment groups using an analysis of variance with site, treatment, age group (infants vs adults) and interactions as factors in the model. Lack of significance (P<0.05) for the age group-by-treatment will be used as justification for pooling the age groups. If the interaction is significant, the age groups will be analyzed separately. If appropriate, non-parametric procedures (e.g. ranking the data prior to analysis) will be used.

The primary analysis will be done using an intent-to-treat (ITT) population, using all subjects who have at least one dose of their assigned product. For this analysis, dropouts will be considered censored at the time of dropping out. Because two primary endpoints are being tested, Hocherg's procedure will be used to determine statistical significance to preserve the Type I error rate of α =0.05.

A second analysis will be done using a per protocol (PP) set. This analysis will be done on those subjects who were compliant with therapy and completed all procedures. This dataset will be defined prior to database lock, and all reasons for exclusion will be documented.

Analytical methods will be defined in detail in the approved Statistical Analysis Plan (SAP).

Secondary efficacy endpoints in this study will include:

- Time to resolution of severe Category 2 IAD, defined as re-epithelialization of skin. The time to resolution will be tested using a Cox Proportional Hazards model, with treatment group as a fixed factor in the model, and center as a random factor in the model. Other important prognostic factors (e.g., age, type and intensity of incontinence, use of corticosteroids, diabetes, use of warfarin) will be identified and may be included as covariates in the model. Kaplan-Meier estimates of time to re-epithelialization will also be done.

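### The primary IAD score is taken at the last visit with no cut-off at Day 21 or at crossover, so comparator subjects who switch can be scored after Cavilon

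*Combined protocol and SAP*

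**What the plan says.** The time point of the primary endpoint is worded in three ways:

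- Section 7.1: "The primary efficacy endpoint will be percent change in IAD score from baseline to end of subject participation".
- Synopsis: "The primary endpoint is percent change in IAD scores from baseline to end of study". Section 5.1 agrees: "The primary endpoint is percent change from baseline to end of study in IAD scores".
- Section 19.1.1: "The percent change from baseline will be calculated at the last visit and compared between treatment groups".

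Section 11.2 says that a subject's "participation in this study is completed after 21-42 -days of follow-up or when the subject is discharged from the facility", and it schedules a skin assessment at that final visit.

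Section 6.4 sets out who stays beyond the first period and on which product. For adults at Day 21, "All subjects will be discontinued at this point with the exception of the following 2 scenarios". The two exceptions are:

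- Comparator subjects who are unhealed and still incontinent "may be crossed over to the Cavilon Advanced Skin Protectant group and allowed to continue for up to an additional 21 days".
- Cavilon subjects who healed or improved, and who are still in hospital and incontinent, may continue on Cavilon for up to 21 more days.

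For children, comparator subjects without improvement within 3 days may switch to Cavilon. Cavilon subjects "who fail to improve (IAD) within 3 days of first application in the study may be discontinued".

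IAD scoring continues after the switch (sections 6 and 16.3, and the Schedule of Events).

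**The concern.** In a superiority trial the primary score should reflect the product to which the subject was randomized, over a period defined in the same way in both arms. As worded, an adult comparator subject who switches after Day 21 and stays to Day 42 contributes a score taken after up to three weeks of Cavilon. A child who switches after 3 days contributes a score taken almost entirely on Cavilon. On the Cavilon side, only subjects who are doing well get the longer follow-up, and pediatric non-improvers may be stopped at about Day 3.

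These decisions are optional, and section 6.2 says the nurse applying the products cannot be blinded. A null result could then be an effect of crossover, and the size of any difference found would be hard to interpret. The sample-size re-estimation in section 19.3 rests on the same primary analysis and would carry the same ambiguity.

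**Working it through.** **1. Does any rule stop the primary score before crossover?**

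| Place | What it limits | Covers crossover? |
|---|---|---|
| 19.1.1 | Dropouts are censored when they drop out | No: switchers remain in the study |
| 12 | Data after a serious pressure ulcer, or once topical treatment is needed | No |
| 19.1.1, switcher analysis | Adds a secondary estimate after switching | No: it does not take those scores out of the primary |
| 19.1.1, per-protocol set | Subjects compliant with therapy who completed procedures | Not clearly |
| 19.4 | Sensitivity analysis that counts dropouts as worsening | No |

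None does.

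**2. Would reading end of study as Day 22 close the gap?** The last column of the Schedule of Events is shared by D22 and D44, so it supports either reading. Even a firm Day 22 reading fails for children, who may switch after about 3 days, inside the first 21 days. The limit must also fall at the first Cavilon application.

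**3. The plan's own sample size.** Section 19.2 gives a difference of 45 points, SD 70, 51 per arm and power of at least 80%. Section 19.3 gives a final two-sided level of 0.0483.

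- Standard error = 70 × √(2/51) = 13.86; noncentrality = 45 / 13.86 = 3.25.
- Two-sample t-test with 100 degrees of freedom: power = 0.892. The stated bound is met.
- 80% power needs 40 per arm. At 51 per arm, power is 0.80 at a true difference of 39.4 points.

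**4. Illustration of dilution by crossover alone.** Let p be the share of the comparator arm scored after switching, and s the share of the 45-point gap that switchers close. Both are assumptions; the documents give neither.

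Expected difference = 45 × (1 − p × s)

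| p | s = 1: difference | Power, 51 per arm | n per arm for 80% | s = 0.5: difference | Power, 51 per arm | n per arm for 80% |
|---|---|---|---|---|---|---|
| 0 | 45.0 | 0.892 | 40 | 45.0 | 0.892 | 40 |
| 10% | 40.5 | 0.821 | 49 | 42.75 | 0.860 | 44 |
| 20% | 36.0 | 0.725 | 61 | 40.5 | 0.821 | 49 |
| 30% | 31.5 | 0.609 | 80 | 38.25 | 0.776 | 55 |
| 40% | 27.0 | 0.482 | 108 | 36.0 | 0.725 | 61 |

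Power reaches 0.80 when p × s = 1 − 39.4/45 ≈ 0.124:

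- Full closure: p ≈ 12% (6 of 51 gives 0.806, 7 of 51 gives 0.788).
- Half closure: p ≈ 25% (12 of 51 gives 0.806, 13 of 51 gives 0.797).

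The model treats switchers as average comparator subjects although they are selected failures. It holds the SD at 70, and it leaves out the Cavilon extension and the early pediatric stops. It therefore does not bound the true effect in either direction.

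**The case against.** The strongest reply is that the protocol already treats 21 days as the main period. Several sections speak of a 21-day follow-up, Days 23-42 have their own case report form column, the Cavilon extension has its own purpose (prevention of recurrence), and efficacy after switching is a separate secondary endpoint. A statistician could reasonably take the primary to be the initial period. This shows a possible intent, but no section states it. Section 7.1 read with section 11.2 says otherwise, and the reading does not help children who switch early.

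Second, section 19.1.1 defers detail to a separate SAP, which was not supplied and may set the cut-off. This stands as a limit on the finding. The protocol would still need aligning, because its own sections use three different terms for the time point.

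Third, scoring everyone at the end regardless of switching can be a legitimate intent-to-treat choice. The plan never says that post-switch scores are included on purpose, however, and follow-up length that varies with arm and response is hard to defend as a policy.

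Fourth, crossover may be rare. Adults must be unhealed, incontinent and still in the facility at Day 21, while entry requires only an expected 7-day stay. At 5% crossover with full closure, power is still 0.86. This also stands, and it is why the conclusion rests on the wording rather than on the power figures.

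**Conclusion.** The concern holds: the endpoint is wrong as written and must be fixed. Following the text gives a primary comparison in which some comparator subjects are scored on the test product, and in which the visit scored depends on arm and response.

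Crossover by itself pulls the arms together if Cavilon works. The extension and the early pediatric stops could push either way, so the net direction and size are unknown. The illustrative loss is from power 0.89 to below 0.80 at about 12% crossover (full closure) or 25% (half closure). The re-estimation in section 19.3 might recover power but not meaning: at 20% crossover with full closure, a larger trial would still estimate 36 points rather than 45.

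Confidence is medium, because the SAP was not available and the crossover rate is not given.

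**What to change.** In the synopsis and sections 5.1, 7.1 and 19.1.1, define the primary endpoint in one form of words: percent change from baseline to the last IAD assessment on the randomized product within the initial 21-day period, in both arms. Then:

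- Count the D22 assessment if it is taken before any crossover or extension application.
- For subjects who cross over, use the assessment taken just before the first Cavilon application.
- Report crossover and extension data as separate secondary results.
- Do not code crossover alone as worsening. It is an optional, open-label decision available only in the comparator arm.
- State as a limitation that, for children who switch or stop at about Day 3, the scored visit still depends on response.
- Make the change without knowledge of unblinded interim results, record its timing relative to the interim analysis, and use the same definition in the sample-size re-estimation.

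Separately, the length of pediatric follow-up must be reconciled. Section 6.4 gives a maximum of 21 days, yet the same section allows 21 more days after crossover, and section 11.1 allows 21 more days of extension.

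The cost is a protocol amendment under section 20.1 in a trial running since fall 2015. No new data are needed. Assessments are already planned three times a week and at D22. The pre-crossover assessment is explicit for children (sections 6.4 and 11.1), and the schedule's D1/D23 column already has a skin assessment for adults entering the second period. The amendment should say that it comes before product is applied. The downside is that crossover and extension data leave the primary analysis and become descriptive. If the SAP already sets this cut-off, only the protocol text needs to change.

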Adult Subjects on the comparative product with ongoing incontinence who fail to heal (reepithelialization of denuded areas) may be crossed over to Cavilon Advanced Skin Protectant for additional 21 days of product application and assessments per the protocol. These subjects will be followed for up to a maximum of 42 days, or until discharged from the facility. During the study followup period, the frequency and intensity of subjects' incontinence will be monitored, and photographic documentation and IAD site assessments will be completed. Pediatric subjects who fail to improve within 3 days on the comparative product may be crossed over to Cavilon Advanced Skin Protectant product for up to 21 days. Pediatric subjects who fail to improve within 3 days on the Cavilon Advanced Skin Protectant may be discontinued from the study.

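### The primary IAD score is taken at a subject's last visit, which can fall at day 42–44, after paste failures have switched to Cavilon or Cavilon improvers have been extended

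*Combined protocol and SAP*

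**What the plan says.** The primary score is timed in three ways, none tied to a day.

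- Synopsis, Outcome Measures: "The primary endpoint is percent change in IAD scores from baseline to end of study". Section 5.1 has the same timing.
- Section 7.1: "The primary efficacy endpoint will be percent change in IAD score from baseline to end of subject participation".
- Section 19.1.1: "The percent change from baseline will be calculated at the last visit and compared between treatment groups".

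Section 11.2 says when that visit occurs: a subject's "participation in this study is completed after 21-42 -days of follow-up or when the subject is discharged from the facility". The last column of the Schedule of Events is headed "End of Study/ D22/D44".

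Section 6.4, item 2, stops adults at 21 days with two exceptions. Paste subjects "who fail to reach healing at the end of 21-day period with ongoing incontinence may be crossed over" to Cavilon. Cavilon subjects who have re-epithelialized or improved, and who are still hospitalized and incontinent, "may continue to receive the Cavilon Advanced Skin Protectant product for up to an additional 21 days to evaluate prevention of IAD reoccurrence". Section 6 adds, for the adult crossovers: "These subjects will be followed for up to a maximum of 42 days, or until discharged from the facility". It provides for continued assessments over that time, so later scores will exist. Children on paste who have not improved within 3 days may also switch.

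**The concern.** The two routes past day 21 are defined by arm and by response. If the last visit supplies the primary score, a paste adult who failed can be scored in the paste arm after up to three weeks on Cavilon. A Cavilon adult who did well can be scored up to three weeks later than a subject who stopped at day 21. The comparison would then mix different follow-up times and, in the paste arm, different products.

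Crossover and extension are legitimate features with their own endpoints (Sections 7.2 and 19.1.1). The difficulty is only that their visits also feed the primary score. The interim analysis and sample size re-estimation in Section 19.3 rest on the same primary analysis.

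**Working it through.** **1. Is there a cut-off elsewhere?** Three sections could supply one.

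- Section 12 limits the data used when a subject develops a serious pressure ulcer or needs topical treatment. It has no matching rule for crossover or extension.
- Section 19.4 covers replaced subjects, missing data and dropouts. A score taken after crossover is observed, so last observation carried forward does not remove it.
- Section 19.1.3 limits the economic analysis to three weeks or less. The primary analysis has no such limit.

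Section 19.1.1 leaves detail to an SAP. No separate SAP text is in the documents supplied, so the check covers these documents only.

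**2. The plan's own figure.** Inputs from Sections 19.2 and 19.3: 51 per arm, SD 70, difference 45, two-sided final alpha 0.0483.

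- Standard error = 70 × √(2/51) = 13.86.
- Power = Φ(45/13.86 − 1.974) = Φ(1.272) = 0.898. With a noncentral t it is 0.892.

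The stated power of at least 80% holds if the 45-point contrast is preserved.

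**3. Shift per paste crossover.** If one paste subject gains g points after day 22, the paste mean moves by g/51:

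- g = 45: 45/51 = 0.88 points.
- g = 100: 100/51 = 1.96 points.

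An example on the Appendix A scale: a score of 60 at baseline, 60 at day 22 and 1 at day 44. The change is 0% at day 22, but a reduction of (60 − 1)/60 = 98.3% at the last visit. That moves the paste mean by 98.3/51 = 1.93 points.

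**4. Both routes together.** The documents give no rates, so k, m and e are assumptions. With k paste crossovers gaining 45 points each, and m extended Cavilon subjects changing by e points each (positive means further improvement):

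Difference = 45 − 45k/51 + m·e/51

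| k | m | e | Difference |
|---|---|---|---|
| 0 | 10 | +20 | 48.9 |
| 0 | 10 | −20 | 41.1 |
| 5 | 10 | +20 | 44.5 |
| 5 | 10 | −20 | 36.7 |

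**5. Power under crossover alone.** Let a fraction f of the paste arm be scored after crossover and recover a share r of the 45-point gap, with the SD kept at 70. The difference becomes 45(1 − f·r).

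| f | Power, r = 1 | Power, r = 0.5 |
|---|---|---|
| 10% | 0.83 | 0.87 |
| 20% | 0.73 | 0.83 |
| 30% | 0.62 | 0.78 |
| 40% | 0.49 | 0.73 |

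The difference that gives exactly 80% power is 39.04. Power therefore falls below 80% at f = 1 − 39.04/45, about 13% (r = 1), or about 26% (r = 0.5).

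**6. Would a day 21/22 cap lose scheduled assessments?** Dosing-day assessments under the four start patterns in Section 10:

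- Monday start: days 1, 3, 5, 8, 10, 12, 15, 17, 19
- Tuesday start: days 1, 3, 5, 7, 9, 11, 14, 16, 18
- Wednesday start: days 1, 3, 6, 8, 10, 13, 15, 17, 20
- Thursday start: days 1, 3, 5, 7, 9, 12, 14, 16, 19

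Each pattern has nine assessments, the last on day 18 to 20. The cap loses none.

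**The case against.** The strongest reply is that a 21-day comparison was plainly meant. Section 6 gives adults 21 days of product unless discharged, Sections 8 and 11.1 speak of a 21-day follow-up, and the case report form periods in Section 16.3 split at day 22/23. The schedule header pairs day 1 with day 23 and so on, which can be read as two cycles, with day 22 closing the randomized one. This is good evidence of intent, but none of it tells the analyst to use the day 22 score. The wording that selects the score points to the last visit.

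Second, intention-to-treat analysis properly keeps switchers in their randomized arm. That is true, and scoring after a switch can be a deliberate choice of estimand. It does not justify reading the outcome at about day 22 for some subjects and day 42–44 for others according to arm and response.

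Third, percent change at each visit is a planned secondary analysis, so results up to day 21/22 would be reported in any case. That helps a reader but does not repair the primary test.

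Fourth, exposure may be small. Eligibility asks only for an expected 7-day stay, discharge counts as completion, healed subjects may stop, and both routes are optional. At 10% crossover with full recovery, power is still 0.83, and crossover alone works against the superiority claim. All of this stands. It limits the likely size but leaves the rule as it is.

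**Conclusion.** The point holds. As written, the primary score can come from day 42–44, and among adults only for paste failures who switched or Cavilon subjects who healed or improved and were extended. Timing and prior product then depend on arm and response.

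The late reading is possible rather than certain, and a separate SAP might settle it. The size is unknown because crossover and extension numbers are not given; the ranges above are illustrations. Paste crossovers who improve on Cavilon narrow the difference. Extended Cavilon subjects may improve further or recur, so the net direction cannot be determined. Children who leave paste at about day 3 raise the same question of which score counts. The sponsor should correct this before the primary analysis.

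**What to change.** In Sections 7.1 and 19.1.1, define the primary score for all subjects as the last IAD assessment no later than the day 21/22 visit and before any adult crossover application. Use later data only for the existing switch and prevention endpoints.

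For children who switch at about day 3, prespecify one of two scores as primary and the other as a sensitivity analysis:

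- the latest score up to day 21/22 regardless of the switch, which is closer to the stated intention-to-treat analysis; or
- the last score before the switch.

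As a separate wording matter, align the pediatric duration in Sections 1, 6.4 and 11.1. The 21-day maximum in 6.4 does not fit the further 21 days allowed elsewhere; Section 6 suggests a 21-day total was meant.

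The cost is one visit-selection sentence in two sections, the pediatric rule with its sensitivity analysis, and the wording alignment. No new data are needed. A day 22 skin assessment is scheduled, and if it is missed in continuing subjects because that column is headed as end of study, the day 18–20 score serves. Under Section 20.1 the change may count as a significant amendment, needing investigator signature and IRB submission, unless it is made in the SAP. The price is that outcomes after day 22 no longer inform the primary comparison.
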